## 5 OBJECTIVES AND OUTCOMES

Table 1: Objectives and outcomes

5.1 PRIMARY OBJECTIVE AND OUTCOME	
Primary objective	Primary endpoint
To determine if ATSB deployment plus universal LLIN coverage is superior to universal LLIN coverage alone in reducing the case burden of clinical malaria in western Kenya	
 
The incidence rate of clinical malaria by the end of year-2, defined as current fever (axillary temperature of <math>\geq 37.5^{\circ}\text{C}</math>) or history of fever in last 48 hours and a positive rapid diagnostic test (RDT, pLDH or HRP2), in children aged 1-<15 years enrolled in the cohort study
 

5.2 SECONDARY OBJECTIVES AND OUTCOMES	
5.2.1 Efficacy	
Secondary objectives	Secondary endpoints
To determine if ATSB deployment plus universal LLIN coverage compared to universal LLIN coverage alone is superior in reducing malaria infection	
 
The time to first malaria infection assessed by PCR by the end of year-2, in children aged 1-<15 years enrolled in a cohort study
 
The incidence rate of malaria infection detected by RDT (pLDH) by the end of year-2, in children aged 1-<15 years enrolled in a cohort study
 
The prevalence of malaria infection diagnosed by RDT in continuous household surveys in participants aged <math>\geq 1</math> month.
 

To determine in ATSB deployment plus universal LLIN coverage compared to universal LLIN coverage alone reduces the clinical case burden in health facilities and communities	
 
The incidence rate of RDT or microscopy confirmed clinical malaria assessed through passive surveillance at health facilities and community-based surveillance by Community Health Volunteers serving the village-clusters
 

To determine if the rate of overall illness events differs in the ATSB deployment plus universal LLIN coverage arm when compared to the control arm	
 
The incidence rate of non-malaria illness in the cohort study
 
The incidence rate of all-cause sick visits assessed through passive surveillance at health facilities and community-based surveillance by community health volunteers
 

To determine if ATSB deployment plus universal LLIN coverage compared to universal LLIN coverage alone reduces malaria transmission or affects insecticide resistance	
 
Entomological outcomes including malaria vector densities, the proportion of females older than three gonotrophic cycles, sporozoite rate, EIR and markers of insecticide resistance
 
Antibodies against merozoite surface protein-1 (MSP-1), circumsporozoite proteins (CSP) and other malaria antigens
 
Molecular measurements including, but not limited to, 24-single-nucleotide polymorphisms (24-SNP) barcodes for the complexity of infection
 
Mosquito salivary antigens for biting rates
 

5.2.2 Safety	
Assess the safety of ATSBs on humans	
 
Adverse events associated with misuse or loss of ATSBs.
 

Assess the safety of ATSBs on non-target insects	
 
Continued entomological monitoring of non-target insect populations
 

5.2.3 Ethnographic evaluation	
To understand the acceptability and potential factors that influence ATSB coverage	
 
The proportion of ATSBs that have been moved/removed
 
The proportion of household heads who perceive ATSBs as safe and effective
 

Assess the acceptability of ATSBs by communities and other stakeholders	
 
Identification of potential barriers to uptake and consistent ATSB coverage,
 
Assessment of the impact of ATSBs on the coverage and use of existing malaria control interventions (e.g. LLIN, IRS, treatment-seeking behaviour)
 

5.2.4 Health economics	
Estimate the cost-effectiveness of deploying ATSBs for malaria control.	
 
Incremental cost-effectiveness of ATSB above the standard of care measured through costing of intervention and efficacy outcomes
 

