#### 6.3.3.1 Cohort study (active case detection)

Participants aged 1 to <15 years who are usual residents of households within a core area of a study cluster will be randomly selected for enrolment into an active cohort (see section 9.1.2, Cohort study to assess the incidence of clinical malaria, page 34). All consented and enrolled cohort members will be given a presumptive treatment course of artemether-lumefantrine to clear any malaria infections. Parasite clearance will be confirmed two weeks after treatment. The scheduled monthly cohort visits will begin one month after the first day of this treatment. During monthly visits, study staff will collect a fingerprick (or heel prick in small infants) blood sample (about 250uL to 1 ml) for dried blood spots on filter paper. Should the cohort member report a fever in the last 48 hours or have an axillary temperature of  $\geq 37.5^{\circ}\text{C}$  at the time of the visit, the study staff member will perform a malaria RDT, and if positive, will treat the participant as per the Kenya Ministry of Health guidelines. A questionnaire will be administered to all cohort members and/or their caregivers to assess for illness, care-seeking, and LLIN usage, among other indicators. Several questions will be asked to monitor for any SAEs. A questionnaire assessing ATSB knowledge, attitudes and perceptions (KAP) will also be administered. Please see section 9.1.7, Rapid ethnographic methods, page 39, for more details.

Figure 4: Overview of activities and procedures in intervention and control areas

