##### 9.1.2.1 *At recruitment/enrolment*

- Informed consent will be administered to the parent/caregiver, and assent to the participant if he/she is 13-<15 years of age
- A fingerprick blood sample (~250µL or 1mL) will be collected to perform an RDT and to prepare approximately five dried blood spots (DBS) on filter paper for subsequent molecular and potentially serological testing and for evaluation of mosquito salivary antigens
- All cohort members will be treated with artemether-lumefantrine (AL; first-line antimalarial in Kenya) irrespective of their RDT result to clear any subpatent infections that may exist
- A questionnaire will be administered to the head of the household to assess household assets for the construction of socio-economic status (SES) categories and to assess household malaria control measures (e.g. number of LLINs, housing construction)
- A questionnaire will be administered to the parent/caregiver and/or the participant to assess activities of interest, including medical and vaccination history, medication use, inclusion in other clinical trials, care-seeking behaviour, LLIN use, daily commuting and travel information, and information about the structure that the participant sleeps in
  - A photograph will be taken of vaccination history and pertinent medical records from the maternal child health booklet or other records

- For participants enrolled in the HDSS or clinical studies, we will link the cohort data to their study/HDSS records
- For young women of childbearing age (12-14 years), pregnancy status will be evaluated in a private and confidential location through the following algorithm:
  - If the woman has had menarche, her last menstrual period was  $\geq 6$  weeks ago, and if she has any suspicion that she may be pregnant, then she will be offered a urine pregnancy test
  - If she declines or is found to be pregnant, she will be considered ineligible for the cohort
- A photograph may be taken of the participant to create a study identification badge that the participant will keep for identification by study staff for scheduled and sick visits

9.1.2.2 *Parasite clearance confirmation visit (2 weeks after enrolment)*

- Before this visit, the study team will call the cohort member to remind them of the upcoming visit and reschedule if necessary. Up to three visit attempts will be made to complete the parasite clearance confirmation visit.

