- Two weeks after the enrolment visit, the household will be visited and a finger-prick blood sample (~250 $\mu$ L to 1mL) will be drawn to prepare five dried blood spots, and to prepare a blood smear for parasite clearance confirmation.
- If the participant is febrile at this visit, the staff member will review the RDT result from the enrolment visit.
  - If the enrolment visit RDT was negative, the participant will be re-tested with an RDT and if positive, the participant will be ineligible for the cohort and second-line antimalarial treatment will be administered as per national guidelines (e.g. dihydroartemisinin-piperaquine). If the RDT administered during this visit is negative, we will proceed with the blood smear.
  - If the enrolment visit RDT was positive, the blood smear will be expedited.
- If the participant is found to be positive for malaria by microscopy, we will consider the participant ineligible for the cohort and will withdraw him/her. A staff member will return to the house to convey this information and provide second-line antimalarial treatment as per national guidelines (e.g. dihydroartemisinin-piperaquine).

9.1.2.3 *At each monthly cohort visit (starting 4 weeks after enrolment)*

- Prior to each follow-up visit, the cohort study team will call cohort members to remind them of the next visit and reschedule, if necessary, to minimize loss to follow-up. Up to three visits will be made to each cohort study household to complete a follow-up visit.
- At each of these visits, a finger finger-prick blood sample (~250 $\mu$ L to 1mL) will be drawn to prepare approximately five dried blood spots for testing, as indicated in the enrolment visit.
- If the participant has an axillary temperature of  $\geq 37.5^{\circ}$  C or reported history of fever in the last 48 hours, a malaria RDT will be performed using blood from the same fingerprick. Those who test positive for malaria by RDT will be treated at the household according to the Kenya Ministry of Health Guidelines unless they already received appropriate antimalarial treatment from other sources in the previous seven days. Cohort members who do not have objective fevers or report a history of fever in the last 48 hours will not be tested for malaria by RDT.

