#### 9.1.2.4 Sick visits (participant initiated visits occurring between scheduled monthly visits)

- Study staff will tend to cohort participants for sick visits as described above
- During these sick visits, study staff will administer a “sick visit” questionnaire including questions about current illness and any associated care-seeking behaviour or medications ingested.
- Questions about physical interaction with or ingestion of ATSBs will also be included for AE and SAE monitoring.
- Will collect a finger- or heel-prick to collect 250 µL to 1 mL of blood to prepare approximately five dried blood spots on filter paper and for any other diagnostic tests that are clinically indicated based on the participant’s presentation
- In the setting of identifying that a cohort member sought care from outside of the study (identified either from a phone call or subsequent scheduled visit), study staff will attempt to gather records from the facility, CHV or pharmacy where the cohort member sought care

PCR and serological testing of the DBS specimens collected during the study will not be used for care.

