##### 9.4.3.1.1 At the time of enrolment

If the blood smear collected two weeks after cohort enrolment (parasite clearance) visit is negative, person-time accrual will begin two weeks after enrolment to account for the post-prophylactic effect of the full treatment course with artemether-lumefantrine

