##### 9.4.3.1.3 Visit following a positive malaria treatment

At the next visit (one month later), if the participant fulfils the criteria for clinical malaria (mRDT positive with symptoms), he/she will again be treated, and two weeks of person-time will be

removed. However, this will only be counted as an event (i.e. contribute to the numerator) if subsequent PCR testing for *P. falciparum* in the laboratory is positive. The rationale for this is based on the long tail of histidine-rich protein-2 (HRP2) antigenemia which can persist for weeks after active infections have cleared, resulting in false-positive mRDT results.

9.4.3.1.4 Visit where participant’s overnight sleeping outside of the cluster of residence is documented

If a person sleeps outside of their cluster of residence for a period to be defined in the Statistical Analysis Plan based on a consensus between the three trials in Kenya (this protocol), Zambia and Mali, person-time and events for that month will be excluded. If the participant is found to be RDT positive, this event will not count in the numerator

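### The cohort endpoint of RDT-detected malaria infection cannot be measured as infection, because follow-up RDTs are done only in febrile or ill children

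*Protocol*

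**What the plan says.** Section 5.2.1 (Table 1) and the registration data table list three endpoints under the objective of reducing malaria infection: PCR time to first infection in the cohort, RDT prevalence in the household survey, and "The incidence rate of malaria infection detected by RDT (pLDH) by the end of year-2" in cohort children. The last has no fever requirement. Fever is what defines the primary endpoint in section 5.1.

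The testing procedure is conditional on fever. Section 6.3.3.1 opens the rule with "Should the cohort member report a fever in the last 48 hours or have an axillary temperature of" the threshold, and only then is an RDT done. Section 9.3.1 says the same. Section 9.1.2.3 adds the negative: cohort members who have no measured fever and do not "report a history of fever in the last 48 hours will not be tested for malaria by RDT".

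The one RDT without a fever condition is at enrolment, where a fingerprick sample "will be collected to perform an RDT and to prepare approximately five dried blood spots (DBS) on filter paper" (section 9.1.2.1). Section 9.4.3.1.1 states that "person-time accrual will begin two weeks after enrolment". At sick visits, blood is taken for dried blood spots and "for any other diagnostic tests that are clinically indicated based on the" child's presentation (section 9.1.2.4).

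**The concern.** An infection endpoint needs infection status whether or not the child is unwell. Here the test is triggered by a symptom that forms part of the primary outcome, so the protocol rules out, at scheduled visits, the measurement that would separate the two endpoints.

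A result reported as malaria infection by RDT would look like independent support for an effect on infection while mostly restating the primary result. The trial is open-label (section 8.2) and a reported fever is enough to trigger a test, so the endpoint would also depend on fever reporting. The results are meant to inform WHO's vector control advisory group (sections 4 and 9.4.1.1), so the label matters.

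The assay is unclear too. The endpoint names pLDH and no procedure names a pLDH test, while section 9.3.1 says the RDTs used in Kenya detect HRP2 and that the main outcomes depend on it.

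**Working it through.** The protocol gives no event rate or sample size for this endpoint, so the check compares its wording with the RDT rule on every occasion when a cohort child is seen.

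| Occasion | RDT rule | Can it record an incident infection in a child who is not ill? |
|---|---|---|
| Enrolment (9.1.2.1) | All children | No. It precedes presumptive treatment and the start of person-time (9.4.3.1.1) |
| Two-week clearance visit (9.1.2.2) | Only if febrile with a negative enrolment RDT | No. A positive makes the child ineligible |
| Monthly visits (9.1.2.3; also 6.3.3.1, 9.3.1) | Only with measured or 48-hour fever | No. Other children are expressly not tested |
| Sick visits (9.1.2.4) | As clinically indicated | No. An ill child without fever might be tested |
| Outside-care records (9.1.2.3, 9.1.2.4) | Whatever the provider did | No. They arise from care-seeking |
| Dried blood spots (9.3.1) | Not an RDT | Collected from all children, but the cohort uses named are PCR, serology, genetics and possible HRP2 work, with no pLDH assay |

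By rule, the number of RDTs at scheduled follow-up visits in children without current or 48-hour fever is zero. The household survey, by contrast, does an RDT with no fever condition (sections 6.3.3.3 and 9.1.3.2), which is what an RDT infection endpoint requires.

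**Overlap with the primary endpoint.** The primary event is fever plus a positive RDT. The plan's expected control-arm count reproduces: 880 person-years × 0.845 = 743.6, stated as 744 (sections 6.2.2 and 7.8.1.1). Most follow-up RDT positives would come from this same pool of febrile, tested children. The two endpoints are not identical. The primary accepts pLDH or HRP2, and for a positive at the visit after treatment "this will only be counted as an event (i.e. contribute to the numerator) if subsequent PCR testing" is positive (section 9.4.3.1.3). No such filter is stated for the infection endpoint.

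**Size of the loss.** If f is the febrile share of RDT-detectable infections at visits, the share missed is 1 − f. The protocol does not give f. Purely as an illustration, assumed values of 0.20, 0.40 and 0.60 give 80%, 60% and 40% missed.

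If f differs by arm, the observed rate ratio is the true ratio × f(intervention) / f(control). With an assumed true ratio of 0.70:

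- 0.70 × 0.50 / 0.40 = 0.875
- 0.70 × 0.30 / 0.40 = 0.525
- equal shares leave it at 0.70

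These show the mechanism. They are not estimates for this trial.

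**The case against.** The best case against is that the endpoint is mislabelled rather than lost. RDT-positive infections are still recorded in febrile children, at some sick visits and in copied outside-care records. Dried blood spots are taken at every monthly visit, so infection status can be recovered in the laboratory. This is one secondary endpoint with no power calculation attached, and two others serve the same objective. Most of this stands, and it limits the seriousness. It does not rescue the endpoint: all those RDT sources concern febrile or ill children, and blood spots tested by PCR are a different endpoint from the one written.

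Two narrower points carry some weight. Section 9.4.4.1.1 applies similar methods to secondary clinical outcomes, so it is unclear, rather than excluded, whether the PCR filter carries over. Its absence could also be deliberate, since the filter is justified by HRP2 persistence. And the primary definition allows pLDH or HRP2, so pLDH readings are contemplated. The HRP2 sentence in section 9.3.1 shows wording to reconcile, not that a pLDH result will be unavailable.

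Finally, section 11.3.4 tells cohort members they benefit from monthly testing for infection, which could suggest that wider testing was once intended. The protocol does not settle this, but the explicit rule in section 9.1.2.3 is what staff would follow.

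**Conclusion.** The concern holds. Followed exactly, the protocol cannot deliver this endpoint as a measure of infection. It would give largely febrile, RDT-positive episodes, close to the primary outcome. An analysis plan cannot repair that, because RDTs that were never done cannot be recovered. One of three endpoints under the infection objective is affected. The primary endpoint, its power and its alpha are not, and PCR time to first infection and household-survey prevalence remain valid for the objective.

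The conclusion rests only on the endpoint wording and the stated testing rule. The share of infections missed is unknown from the document. This should be fixed, but it does not threaten the trial's main conclusion.

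**What to change.** Choose one of two changes.

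1. Delete the endpoint and let PCR time to first infection and household-survey RDT prevalence carry the infection objective.
2. Redefine it as infection incidence by PCR or a laboratory antigen assay on the dried blood spots already collected. This needs a rule for what counts as a new infection after a positive result. Section 9.1.2.4 states that "PCR and serological testing of the DBS specimens collected during the study will not be used for care", so consecutive positives may be one persisting infection.

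Merely relabelling it as febrile RDT-positive episodes would be accurate but would add little to the primary endpoint.

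Either way, reconcile the pLDH and HRP2 wording across the registration table, Table 1 and section 9.3.1, and reconcile the monthly-testing statement in section 11.3.4 with sections 6.3.3.1 and 9.1.2.3. No change to the RDT testing or treatment rule is proposed.

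Deletion costs only wording changes in the registration table, Table 1 and sections 9.3.1 and 11.3.4. Redefinition adds the new-infection rule and some laboratory runs beyond the PCR already planned, with no new blood sampling. Either is a protocol amendment and needs the approvals in section 11.2.2.

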## 6 TRIAL DESIGN AND DESIGN CONSIDERATIONS

---

### 6.1 OVERVIEW OF STUDY DESIGN

This will be a phase III, open-label two-arm cluster randomized controlled superiority trial (CRCT) with a 1:1 allocation ratio to compare ATSB + LLINs vs LLINs alone (standard of care).

During the baseline year, 100 clusters will be followed for 1-year. Clusters consist of approximately 1 to 3 contiguous villages to achieve an optimal cluster size of between 200-400 households per cluster. Clusters are divided into core and buffer areas, as described in Section 6.2.3, Measures to avoid contamination, page 17. The sampling frame for measuring baseline and main study outcomes will be restricted to permanent residents residing in households within each cluster's core area to reduce contamination. After the baseline period, 80 out of the 100 clusters will be allocated to one of the two arms using restricted randomization based on the optimal combination of options that minimizes imbalance in baseline predictors between study arms.

The study is designed to detect a  $\geq 30\%$  reduction in the primary outcome over two years, which is the incidence of clinical malaria in a cohort of children aged 1-15 years, defined as current fever (axillary temperature of  $\geq 37.5^{\circ}\text{C}$ ) or history of a fever in the last 48 hours and a positive RDT. The WHO considers this effect size to be the minimal reduction required worthy of a WHO recommendation. The prevalence surveys will also be powered to detect a 30% reduction in malaria prevalence by RDT each year.

## 6.2 DESIGN CONSIDERATIONS

### 6.2.1 Superiority trial to detect at least a 30% reduction

The study is designed as a superiority trial to detect at least a 30% reduction compared to the current standard of care (universal coverage of LLINs) over a two-year period, which is the minimum reduction considered worthy of a WHO recommendation and large-scale deployment.

### 6.2.2 Duration of trial, interim analysis and criteria for early termination

This study in Kenya is part of three similar trials conducted in Kenya (this protocol), Zambia and Mali. The purpose of these trials is to inform the assessment of public health value by WHO's Vector Control Advisory Group (VCAG). This requires at least a single year of data, but ideally, two years [16-18]. This trial in Kenya is designed to have two interim and one final analysis, i.e. a total of three looks. The main purpose of these interim analyses is to inform WHO's recommendation making process in a timely manner. In brief, the interim analyses will occur either after 50% and 75% of person-time have completed (i.e., after about 1 and 1.5 years respectively), or after 50% (n=372) and 75% (n=558) of the total number of expected primary outcome events over two years in the control arm (n=744) have occurred (whichever comes first). The number of events will be tracked by an independent statistician not involved in the trial. Whether the interim analysis results will lead to the early stoppage of this trial, e.g., for futility or overwhelming evidence of efficacy, will depend on the overall evidence from the three trials. Please see Section 9.4.1, Interim analysis, page 44, for details of the interim analysis's purpose and procedures.

